Congenital malformations are structural abnormalities of prenatal origin and can be classified into three groups based on their cause: genetic, environmental or multifactorial (e.g., twinning) [6]. Most congenital malformations (i.e., structural birth defects) result from abnormal development during embryogenesis [7]. The present study is being designed to assess maternal and newborn safety after progestogen exposure in early pregnancy. It aims to accurately characterize the demographic profile of users of progestogens in early pregnancy including past gynecological and obstetric history, indication for progestogen use (specific focus will be given to documenting use during IVF/ART and as treatment for bleeding in early pregnancy or recurrent pregnancy loss), type of progestogen and detail of the course of pregnancy, birth outcome and newborn health. A comparison of live birth rates and rate of malformations in fetus and newborn will be based on indication area and by treatment (dydrogesterone, other progestogens, or other treatment). In keeping with regulatory requirements, reportable adverse drug reactions will be relayed to the relevant marketing authorization holders (MAHs).

4.1 Primary Objectives:

- Assess the rate of major malformations in fetus and newborns by indication and by exposure to progestogens *during the first trimester of pregnancy*, with an emphasis on dydrogesterone versus non-dydrogesterone treatments.

4.2 Secondary Objectives:

- Describe the rate of other malformations by progestogen type and indication of use,
- To describe demographic, reproductive, and maternal health data, as well as available information on prenatal diagnostics and pregnancy outcome for the mother and the newborn.

4.3 Explorative Objectives:

- Characterize the hormonal and non-hormonal utilization patterns of dydrogesterone and non-dydrogesterone treatment in study participants and describe captured background risk scenarios which may serve as causal factors for major fetal and newborn malformations, not only limited to start and stop dates for all products taken during pregnancy, but also including duration, and indication,
- Describe the rate of (spontaneous) miscarriage,
- Describe the rate of induced abortions which may be attributed to maternal health or malformations in the fetus.

5 Research methods

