5.3 Definition of outcome parameters

5.3.1 Definition major malformations

Malformations of primary interest are:

Congenital malformation	
Central nervous system	Respiratory system
Agenesis of the corpus callosum Arhinencephaly / Holoprosencephaly Hydranencephaly Hydrocephaly Macrocephaly Meningoencephalocele Microcephaly Neural tube defect (anencephaly, spina bifida, craniorachischisis) Porencephaly Syringomyelia	Branchial cleft cyst Congenital cystic malformation Larynx hemangioma Pulmonary hypoplasia
Head and neck	Digestive system
Oral Cleft palate without cleft lip Cleft lip with or without cleft palate Eye Anophthalmos Ankyloblepharon Dacryostenosis Ectropion / Entropion Epibulbar dermoid Exophthalmos congenital Glaucoma Nystagmus Persistent Hyperplastic Primary Vitreous Other Anotia/microtia Choanal atresia Congenital hearing loss/disorder	Annular Pancreas Anorectal atresia / stenosis Bile duct atresia Diaphragmatic hernia Esophageal diverticulum Imperforate anus Hepatomegaly Hirschsprungs disease Intestinal Malrotation Microcolon Meconium ileus/plug Obstruction by fibrous band Oesophageal atresia / stenosis Persistent omphalomesenteric duct Pyloric stenosis Pylorospasm

Dysmorphic facies Facial palsy/asymmetric crying facies Hemifacial microsomia Macroglossia Potter facies Torticollis	Rectovaginal fistula Small intestine atresia / stenosis Splenomegaly Tracheo-oesophageal fistula
Cardiovascular system	Skin
All congenital cardiovascular malformations are of interest, excluding : Heart murmur Systolic murmur Haemangioma The following three events will be evaluated at the interim analysis, and if these are still of primary interest further evaluations will be undertaken: Persistent Atrial septum defect Persistent Patent foramen ovale Persistent Patent ductus arteriosus	Abnormal skin findings, excluding : Hyperpigmented/ hypopigmented macules Scars / lesions Skin tags Ichthyosis
Urinary system	Reproductive system
Bladder/urethral diverticulum Congenital cystic kidney disease Enlarged kidney Hydroureter/hydronephrosis Hypospadias Other congenital bladder anomaly Patent/persistent urachus Prolapsed bladder Prune belly Renal agenesis Renal (hypo)dysplasia Renal stones Vesicoureteral reflux	Cliatoromegaly Cryptorchism Ovarian cysts Epispadias Hermaphroditism Small penis Torsion of testis Pseudohermaphroditism Other congenital genitourinary abnormality
Musculoskeletal system	Genetic / chromosome

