Abnormal palmar/plantar creases Arthrogryposis Bowed long bones / missing bones Congenital foot malformation Congenital hand malformation Craniosynostosis Genu valgum/genu varum Hip dislocation/Hip dysplasia Joints in abnormal positions Kinematic imbalances due to suboccipital strain (KISS) Limb reduction defects Pectus abnormalities Polydactyly Scoliosis without vertebral anomalies Sprengel deformity Syndactyly Various head shape abnormalities (Ex: plagiocephaly) without craniosynostosis	Down syndrome Genetic syndromes + microdeletions Klinefelter syndrome Trisomy 13 Trisomy 18 Turner's syndrome
	Other
	Amniotic bands Aplasia Ascites/Anasarca/Hydrops Cysts of various organs Cystic lymphangioma Gastroschisis Hemihyperplasia/ hemihypertrophy Inguinal hernia Lymphangiectasias Multiple congenital abnormalities Omphalocele Situs inversus

These listed malformations will be identified during follow-up, i.e., major malformation in the fetus, and after delivery, i.e., major malformation diagnosed in newborns (i.e., pre- and postnatally diagnosed malformations).

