5.3.2.2 Variables to determine the secondary objective

- Rate of other malformations in fetus and newborn
- Progestogen intake in first trimester for each indication
- Indication of use
- Baseline information
 - Age
 - BMI
 - Race
 - Region of residence
 - Socioeconomic status (SES)
 - Other (cf. section 5.3.2.4.)
- Pregnancy outcome
- Newborn health e.g. NICU admission, prematurity, weight/height newborn at delivery
- Maternal health during pregnancy e.g., obstetric disease, lifestyle (smoking and alcohol), infection, pregnancy-related complication

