5.5 Study size

Two independent cohorts will be considered in the analysis: (A) study participants with bleeding in early pregnancy and/or recurrent pregnancy loss and (B) study participants receiving IVF / ART. Sample size calculations for both cohorts are similar as based on an incidence proportion of major malformation at birth of 200 per 10,000 births for both indications [10–14]. It is expected that dydrogesterone is associated with a risk of major malformation that is not higher than the risk associated with non-use of dydrogesterone. The study is powered to test the non-inferiority of dydrogesterone treatment.

Assuming a drop-out rate of 20% and a rate of major malformation in fetal newborn of 0.02, sample size calculations show that approximately 5,500 study participants per cohort are statistically sufficient (power = 90%, one-sided $\alpha = 0.025$) to exclude a 2.0-fold risk (Odds Ratio) in the dydrogesterone cohort. The test statistic used is the one-sided Score test [15].

Table 1 and Table 2 show proposed sample sizes for sub-group specific allocation rates.

Cohort A: bleeding in early pregnancy / recurrent pregnancy loss

Table 1: Group allocation: 30% (dydrogesterone) versus 70% (reference)

Endpoint	Incidence proportion		Non-inferiority OR	Effective sample size		20%-Drop-out inflated sample size	
	Reference	DYD		Reference N ₁	DYD N ₂	Reference N ₁	DYD N ₂
Major malformation	0.02	0.02	2.0	3,136	1,343	3,920	1,679

Cohort B: IVF/ART

Table 2: Group allocation: 50% (dydrogesterone) versus 50% (reference)

Endpoint	Incidence proportion		Non-inferiority OR	Effective sample size		20%-Drop-out inflated sample size	
	Reference	DYD		Reference N ₁	DYD N ₂	Reference N ₁	DYD N ₂
Major malformation	0.02	0.02	2.0	2,059	2,059	2,574	2,574

The total number of study participants will be 11,000 across all geographical study sites China, Turkey and Russia.

Sample size has been calculated using the Statistical Software PASS 2021 Power Analysis & Sample Size [16].

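### The primary outcome list in section 5.3.1 counts entries that do not meet, or need not meet, the section 4 definition of a malformation, and validation does not screen them out

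*Protocol*

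**What the plan says.** Protocol section 4 opens with a definition: "Congenital malformations are structural abnormalities of prenatal origin". It goes on to allow genetic, environmental and multifactorial causes.

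Section 5.3.1 lists the malformations of primary interest, and 5.3.2.1 makes that list the primary variable. Among the entries are:

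- **Musculoskeletal:** "Kinematic imbalances due to suboccipital strain (KISS") and "Various head shape abnormalities (Ex: plagiocephaly) without craniosynostosis".
- **Digestive:** "Pyloric stenosis Pylorospasm" (two adjacent entries).
- **Urinary:** "Renal stones Vesicoureteral reflux" (again two entries).
- **Eye and reproductive system:** nystagmus and torsion of testis.

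The list states no criterion for major and none for prenatal origin. It does screen in places: murmurs are excluded from the cardiovascular group and skin tags from the skin group, and three cardiac entries are set aside for re-evaluation at the interim analysis. Both prenatal and postnatal diagnoses count, and the last questionnaire comes 6-12 weeks after the estimated date of delivery.

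Section 5.2.3 validates reported primary events. Its four classes (definite, probable, possible, not confirmed) grade how certain the diagnosis is.

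A secondary variable already exists in 5.3.2.2: "Rate of other malformations in fetus and newborn".

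**The concern.** The endpoint as listed is wider than the endpoint as defined. KISS and pylorospasm describe function, not structure. Renal stones, nystagmus, torsion of testis and non-synostotic head shape may be congenital or acquired, and nothing in the protocol limits them to the congenital form at validation. A medically confirmed case of any of them is therefore a primary event.

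This matters because of the direction of the test. Section 5.7.2 sets the null hypothesis at OR ≥ 2 and the alternative at OR < 2. In a superiority test, events unrelated to exposure would make an effect harder to show. Here they bring the composite odds ratio closer to 1 and make it easier to reject the null. A real doubling of genuine malformations could then pass as non-inferior more often than the nominal 2.5%.

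**Working it through.** **Inputs from section 5.5.** Reference rate 0.02 (the planning assumption is an "incidence proportion of major malformation at birth of 200 per 10,000 births for both indications"), margin OR 2.0, one-sided alpha 0.025, score test. Effective sizes, reference / dydrogesterone: cohort A 3,136 / 1,343; cohort B 2,059 / 2,059.

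**The plan's own figures.** The dropout step reproduces: 3,136/0.8 = 3,920; 1,343/0.8 = 1,678.75, so 1,679; 2,059/0.8 = 2,573.75, so 2,574. The effective sizes do not reproduce exactly. With no true difference, an odds-ratio score test has exact power of 87.3% (A) and 87.1% (B) at those sizes, against the stated 90%. An unstated software option may explain this, and it does not bear on the present point.

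**Input the protocol does not give.** Let f be the share of reference-group events that come from entries failing the section 4 definition. It is an assumption and is shown as a range. With no effect, the expected primary events are (3,136 + 1,343) × 0.02 = 89.6 in A and (2,059 + 2,059) × 0.02 = 82.4 in B. A share of 10% is thus about 8 or 9 events per cohort.

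**Model.** The total reference rate stays at 2%. Genuine malformations have OR 2.0, the null boundary. Stray events have the same absolute rate, 0.02f, in both groups.

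- Genuine reference rate g = 0.02(1 − f).
- Genuine dydrogesterone rate h = 2g/(1 + g), which gives OR 2.0 exactly.
- Composite dydrogesterone rate p = h + 0.02f.
- Composite OR = [p/(1 − p)] / [0.02/0.98].

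**Example, f = 10%.** g = 0.018. h = 0.036/1.018 = 0.03536. p = 0.03536 + 0.002 = 0.03736. Composite OR = (0.03736/0.96264)/0.02041 = 1.90.

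The probability that the score test declares non-inferiority was then found by exact binomial enumeration at the effective sizes.

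The last column gives the genuine OR that corresponds to a composite OR of exactly 2.0. The dydrogesterone rate is then 0.03922, the genuine part is 0.03922 − 0.02f, and its odds are divided by the odds of g.

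| Share f | Composite OR | False non-inferiority, A | B | Genuine OR when composite is 2.0 |
|---|---|---|---|---|
| 0% | 2.00 | 2.5% | 2.6% | 2.00 |
| 5% | 1.95 | 3.3% | 3.5% | 2.05 |
| 10% | 1.90 | 4.4% | 4.7% | 2.11 |
| 20% | 1.80 | 7.5% | 7.9% | 2.24 |
| 40% | 1.60 | 19.2% | 19.9% | 2.65 |

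The calculation is for the crude comparison. The planned adjusted or weighted analysis would alter the figures, but adjustment does not remove unrelated events from the outcome.

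**The case against.** Several points against this are fair.

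**The list can be read charitably.** It is headed as congenital malformation, so each entry could mean the congenital form, and postnatal diagnosis is not postnatal origin. A head shape abnormality is structural; only its prenatal origin is open, so it is a weaker example than KISS or pylorospasm. This stands, and it is why the ambiguous entries call for a criterion and not for removal. It does not rescue the two entries that are functional as worded, and no validation step enforces the charitable reading.

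**The bias is conditional.** Dilution needs the stray events to have an odds ratio near 1. Treatment is not randomised, and section 5.9 itself warns of confounding and channeling. If these events differ between groups, the bias can go either way. This stands.

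**The effect may be small.** No share is given. At 5% the error rate moves only from 2.5% to about 3.5%, and the clearly functional entries alone could contribute less. This also stands.

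**A broad list is defensible in a safety registry.** Narrowing it may miss unexpected harm. Keeping the full list as a sensitivity analysis answers this.

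Three stronger inferences are tempting but not supported:

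- A reader might infer that first-trimester exposure cannot cause the listed items. Section 4 sets no such test; it speaks of structure and prenatal origin and leaves cause open.
- A reader might infer that the 2% planning rate describes a different event. The rate comes from cited sources that the protocol does not break down, so what they counted is unknown.
- A reader might infer that the error rate approaches one half. It reaches about 49% only if stray events add 2 percentage points on top of 2%, that is, if they are as frequent as all genuine malformations together. Nothing in the protocol suggests this.

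Genetic and chromosomal entries are not part of the point, because the section 4 definition covers them.

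**Conclusion.** The inconsistency is in the text: section 4 requires structure and prenatal origin, 5.3.1 counts entries that lack one or need not have the other, and 5.2.3 does not filter them. The likely statistical consequence is an anti-conservative dilution of the primary odds ratio. If the stray events are unrelated to exposure and make up 5-20% of a 2% total, the chance of a false non-inferiority conclusion at the null boundary is about 3.5-8% instead of 2.5%; at 40% it is 19-20%. Put the other way, excluding a composite OR of 2.0 would exclude only a genuine OR of about 2.05-2.24 at shares of 5-20%.

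The size is unknown and may be modest. The protocol does not show that non-inferiority will be too easy to claim, only that the endpoint leaves room for it. The correction is worth making because it is cheap and the primary list is fixed in the protocol itself.

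**What to change.** 1. In 5.3.1, move the entries that are not structural as worded (KISS, pylorospasm) to the other-malformations category in 5.3.2.2.
2. For entries that may be congenital or acquired (for example renal stones, nystagmus, torsion of testis, head shape abnormalities without craniosynostosis), count a case as primary only if validation classes it as structural and of prenatal origin. Add this classification to 5.2.3 and make it blind to treatment. Section 7 has the same validation team judge drug relationship, so the blinded step needs a separate assessor or must come first.
3. Settle the list and the criterion before outcome data by exposure are seen.
4. Report the full current list as a sensitivity analysis.

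**Cost.** A table edit, one extra field at validation with its blinded procedure, and one sensitivity analysis. The questionnaires are unchanged, though origin may need a closer look at the medical records already being requested.

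There will be fewer primary events and some loss of power. If the planned 2% had included the removed events, the primary rate falls to 0.02(1 − f). With no true difference, exact score-test power at the effective sizes goes from about 87% to about 85% at f = 5% (rate 1.9%), 84% at 10% (1.8%) and 79% at 20% (1.6%), in either cohort. If the share is small, so is this loss.

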Global Ethics Approval	September 2021
Registration in the EU PAS register	October 2021
Start of data collection (First Patient In)	December 2021
End of data collection (Last Patient Last Follow-Up)	April 2024
Study interim/progress report 1	March 2022
Study interim/progress report 2	December 2022
Study interim/progress report 3	September 2023
Data base lock	August 2024
Final report of study results	November 2024

3 Rationale and background

Progestogens are commonly prescribed to women for the indication of luteal phase support (LPS) during IVF (in vitro fertilization)/ART (assisted reproductive technology) treatment, when presenting with early pregnancy bleeding or recurrent pregnancy loss. While miscarriage is a frequent complication of early pregnancy (estimated to occur in 10–20% of pregnancies), recurrent miscarriage is less common, with prevalence estimates varying between 0.8% recurrent miscarriage is less common, with prevalence estimates varying between 0.8% and 3% [1]. Recommendations for treatment options for miscarriage differ between guidelines, largely a result of the guidelines being continually updated in line with the latest clinical evidence. In practice,

the onus is on the prescribing physician to ensure their practices are based on the most recently available data and local recommendations. After 60 years of availability on the market, the available clinical and post-marketing safety data have indicated that dydrogesterone has a favorable benefit-risk profile in the approved indications. However, recent implications and isolated claims by individuals within the scientific community [2–5] have raised some questions related to the safety of dydrogesterone, including a retrospective cohort study suggested an increased risk of major cardiac malformations in newborns exposed to dydrogesterone [3]. The study was methodologically flawed and has since been retracted by the publishing journal.

This registry study aims to establish a scientifically sound pregnancy and newborn safety data set to document any putative teratogenic risks upon exposure to progestogens. A large sample size registry with detailed characterization of participants' background, treatment and pregnancy outcome will provide generalizability and precision in addition to possible future regulatory requests from health authorities.

4 Research question and objectives

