5.3.2 Variables

5.3.2.1 Variables to determine the primary objective

- Rate of major malformations (as defined in section 5.3.1.) in fetus and newborn

- Prescribed treatment in first trimester for each indication
- Indication of use
- Risk factors and potential confounders as per section 5.3.2.4.

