5.7.2 Primary analysis

The primary analysis cohorts are defined as pregnant women using (I) dydrogesterone during the first trimester versus (II) other treatment and/or treatment combinations and/or no treatment during the first trimester as defined in section 5.1. Further analyses on subcohorts of (II) will be considered as secondary or sensitivity analyses. The safety conclusions regarding risk of major malformation will be based on the “as treated” (AT) population analysis set whereby outcomes of interest are assigned to the treatment used during the first trimester of pregnancy.

The overall incidence of major malformation will be calculated with respect to all pregnancies observed in the respective cohort and compared per indication area.

The null hypothesis is defined as odds ratio (OR) for major malformation $H_0: (OR_{MM}) \geq 2$ obtained from a comparison of the primary analysis cohorts. The alternative hypothesis is defined as $H_A: OR_{MM} < 2$, respectively.

The risk of major malformation as compared between treatment cohorts will be assessed by unconditional logistic regression. Potential factors of influence, potential confounding factors or risk factors, will be considered either in a pre-analysis step regarding cohort balancing using methods based on propensity scores, e.g., inverse probability of treatment weighting (IPTW) or by subsequent inclusion into the logistic model as cofactors for adjustment of the treatment effect. Crude and adjusted OR and 95% confidence intervals (CI) will be estimated.

All statistical details including derived variables content of tables and proposed format will be detailed in the SAP.

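### Chromosomal and genetic syndromes count in the primary outcome; if about balanced between groups, they pull the odds ratio towards 1 and make a doubling of exposure-related malformations easier to exclude wrongly.

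*Protocol*

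**What the plan says.** Protocol section 5.3.1 opens its table with "Malformations of primary interest are". One group of that table, for genetic and chromosomal conditions, reads "Down syndrome Genetic syndromes + microdeletions Klinefelter syndrome Trisomy 13 Trisomy 18 Turner's syndrome". Section 5.3.2.1 makes the primary variable "Rate of major malformations (as defined in section 5.3.1.) in fetus and newborn", with no exception for that group.

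This composite is what section 5.7.2 tests (null hypothesis: odds ratio of 2 or more) and what section 5.5 sizes the study on, "to exclude a 2.0-fold risk (Odds Ratio) in the dydrogesterone cohort". In the as-treated analysis, "outcomes of interest are assigned to the treatment used during the first trimester of pregnancy".

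The study's purpose, in section 3, is "to document any putative teratogenic risks upon exposure to progestogens". Section 4 says that congenital malformations "can be classified into three groups based on their cause: genetic, environmental or multifactorial". No section removes genetic cases from the primary comparison. The further analyses named in section 5.7.2 divide the comparator group, not the outcome.

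**The concern.** Constitutional trisomies, sex-chromosome aneuploidies, microdeletions and inherited syndromes are present from conception or the first cell divisions. Women enter this study after treatment of a pregnancy that already exists: bleeding or recurrent loss with evidence of an intrauterine pregnancy, or support after embryo transfer (section 5.2.2.1). Treatment started then cannot have caused these conditions, so counting them says nothing about teratogenic risk.

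The direction matters because of the hypothesis. In a superiority test, events that cannot respond to exposure make the test conservative. Here the conclusion sought is an odds ratio below 2.0, so such events, if balanced, push the estimate towards that conclusion. At stake is how often the study would report a doubling as excluded when the malformations that exposure could cause are in fact doubled.

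**Working it through.** **Inputs from section 5.5.** Reference rate 0.02; margin OR 2.0; one-sided alpha 0.025; score test; 5,500 per cohort; 20% drop-out; allocation (reference:dydrogesterone) 70:30 in cohort A and 50:50 in cohort B.

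Evaluable per cohort: 5,500 × 0.8 = 4,400, which is 3,080/1,320 in A and 2,200/2,200 in B.

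**Assumption.** A share f of reference events is chromosomal or genetic. The documents give no figure, so a range is shown.

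**The plan's own figures.** The drop-out inflation reproduces: 3,136/0.8 = 3,920; 1,343/0.8 = 1,679; 2,059/0.8 = 2,574. The stated 90% power does not. At the stated effective sizes, the exact score test on the odds ratio has 87.3% (A) and 87.1% (B). That is a separate matter, but it is why the power figures below start under 90%.

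**Dilution formula.** Let g(p) = 2p/(1 − p + 2p), the risk when the odds of p are doubled. With genetic events equally frequent in both groups:

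- reference risk = 0.02
- dydrogesterone risk = 0.02f + g(0.02(1 − f))
- composite OR = odds of the dydrogesterone risk divided by (0.02/0.98)

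Example, f = 10%: the remaining reference risk is 0.018. Doubling its odds gives g(0.018) = 0.036/1.018 = 0.03536. Adding 0.002 gives 0.03736, whose odds are 0.03881. The composite OR is 0.03881/0.02041 = 1.90.

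**Chance of declaring non-inferiority when the remaining malformations have a true OR of 2.0** (exact binomial enumeration of the score test):

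| Assumed f | Dydrogesterone risk | Composite OR | Cohort A | Cohort B |
|---|---|---|---|---|
| 0% | 0.03922 | 2.00 | 2.5% | 2.6% |
| 2% | 0.03885 | 1.98 | 2.8% | 3.0% |
| 5% | 0.03829 | 1.95 | 3.3% | 3.6% |
| 10% | 0.03736 | 1.90 | 4.4% | 4.8% |
| 20% | 0.03550 | 1.80 | 7.4% | 8.3% |
| 30% | 0.03361 | 1.70 | 12.1% | 13.6% |

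At the protocol's effective sizes (3,136/1,343 and 2,059/2,059) the results are close: 4.4% and 4.7% at f = 10%, 12.3% and 12.9% at f = 30%.

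Put the other way, a composite OR of exactly 2.0 corresponds to an OR on the remaining malformations of 2.05, 2.11, 2.25 and 2.42 at f = 5, 10, 20 and 30%.

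**If genetic events are not balanced.** Let them be k times as frequent under dydrogesterone, with f = 10%. The dydrogesterone risk is then 0.002k + 0.03536.

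- k = 0.5: risk 0.03636, composite OR 1.85, so more dilution than in the balanced case.
- k = 1.5: risk 0.03836, composite OR about 1.95; chance 3.2% (A) and 3.5% (B).
- k = 2: risk 0.03936, composite OR about 2.01; chance 2.3% (A) and 2.5% (B), so no inflation.

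**Away from the margin.** With a true OR of 3 on the remaining malformations, the chance of declaring non-inferiority stays below 0.2% even at f = 30%.

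**Power if these events are removed** (true OR 1, f = 10%, rate 0.018): 86.9% falls to 83.2% in A, and 89.0% to 85.8% in B. The error at a true OR of 2.0 returns to about 2.5%.

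**The case against.** Four objections carry weight.

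- **The share may be small.** Age is capped at 35, and the section 5.3.1 list is very broad: it takes in inguinal hernia, hip dysplasia, torticollis and head-shape abnormalities. Both favour the low end of the range, where the effect is modest. This stands.
- **An odds ratio of 1 for these events is not assured.** Treatment is not randomised, and section 5.9 itself expects channelling. A treatment meant to sustain pregnancy could also alter which affected pregnancies survive to be detected, without causing the condition. This stands too: the bias towards 1 is conditional. It does not argue for keeping the events, since they would then carry confounding or selection rather than a teratogenic effect.
- **The stated test keeps its level.** Its null concerns the composite of section 5.3.1. When the composite OR is 1.90 that null is false, and rejecting it is not a type I error. A reader might infer from the table that the planned test exceeds its alpha; it does not. The rates are errors about the teratogenic question that the study is meant to answer.
- **Section 4 is not a contradiction.** A reader might infer that, by naming genetic causes separately, the protocol promised to exclude them. It only classifies causes. An all-inclusive rate is a legitimate descriptive quantity; it is a poor basis for the non-inferiority claim.

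A sensitivity analysis without genetic cases may be in the statistical analysis plan, which is not at hand, so its absence here is not held against the protocol. The primary definition, however, is fixed in the protocol.

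**Conclusion.** The concern holds in a conditional form. The primary outcome counts conditions that treatment of an established pregnancy cannot cause. If these are about equally frequent in both groups, they move the odds ratio towards the non-inferiority conclusion. A true doubling of the remaining malformations would be excluded in about 3.3 to 4.8% of studies at an assumed share of 5 to 10%, and in about 7 to 14% at 20 to 30%, against 2.5% intended.

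The result rests on the assumed share, on balance between groups, and on the 0.02 rate describing the full list, which the protocol does not state. The documents do not support treating the 20 to 30% figures as expected, or the direction of bias as certain. The harm lies close to the margin; a tripling would still be caught. This is a should-fix point.

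**What to change.** Define the primary outcome as major malformations excluding cases with a confirmed chromosomal or known genetic diagnosis. Apply the exclusion to the case, not only to one group of the table; otherwise a heart defect in a fetus with a trisomy would still count under the cardiovascular group. Keep multiple-defect cases that have no such diagnosis, since a teratogen can produce them; a restriction to non-syndromic malformations would be too broad. Report the genetic and chromosomal group separately by treatment, and keep the full section 5.3.1 list as a sensitivity analysis.

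The change is to wording in sections 5.3.1, 5.3.2.1 and 5.7.2, and uses diagnoses already collected and validated (sections 5.2.3 and 5.3.2.4).

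There are two costs. First, the protocol plans no systematic genetic testing, so confirmation may vary by country or group; the sensitivity analysis on the full list guards against this. Second, there are fewer events. At 10% fewer, power falls as shown above; at 20% and 30% fewer it is about 79% and 74% at the protocol's effective sizes. Section 5.5 should therefore say whether 0.02 includes genetic cases, and restate the rate and the power for the narrower outcome.
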